## SUMMARY OF CHANGES TO THE PROTOCOL

The protocol history is below:

Version and Date of Protocol	Comments
Version 1.0, 01 March 2021	Original version
Version 1.1, 16 June 2021	Global
Version 1.2, 17 November 2021	Netherlands only
Version 2.0, 24 January 2022	Global
Version 3.0, 10 March 2022	Global
Version 4.0, 05 December 2022	Global
Version 5.0, 22 June 2023	Current version

Key changes in the current version (5.0) of the protocol are summarized below.

Typographical, formatting, and administrative changes were also made to improve the clarity of the document (as applicable).

## 1. SYNOPSIS

Name of Sponsor/Company: Rhythm Pharmaceuticals, Inc.	
Name of Investigational Product: Setmelanotide	
Title of Study: A Phase 3 Multi-Center, One-Year, Open-Label Study of Setmelanotide in Pediatric Patients Aged 2 to <6 Years of Age with Rare Genetic Causes of Obesity	
Trial center(s): Approximately 5 to 8 centers in North America, Europe and/or Asia Pacific	
Studied period (years): One year Estimated date first patient enrolled: February 2022 Estimated date last patient completed: September 2023	Phase of development: 3

Trial Objectives:
 
Primary: The primary objective of the trial is: To evaluate the effect of setmelanotide on weight-related parameters in pediatric patients aged 2 to <6 years with obesity due to either (1) biallelic variants of the POMC, PCSK1, or LEPR genes or (2) Bardet- Biedl Syndrome (BBS).
 
Secondary: The secondary objectives of the trial are: To evaluate the effect of Setmelanotide on additional weight-related parameters, as well as safety and tolerability in pediatric patients aged 2 to <6 years with obesity due to either (1) biallelic variants of the POMC, PCSK1, or LEPR genes or (2) BBS.
	

Methodology: This is a 1-year, open-label trial.
 
Screening The Screening Period begins with obtaining informed consent from the parent or guardian and will last between 1 and 8 weeks. During the Screening Period, patients will undergo all procedures as outlined in the Schedule of Assessments (SoA; Table 1) to determine if they meet all of the Inclusion and none of the Exclusion criteria of the trial. During the Screening Period, patients will undergo medical evaluation; and caregivers will receive training on injection of trial drug and other trial procedures.
	

**Enrollment and trial procedures**

At the enrollment visit, patients will undergo all procedures as outlined in the SoA (Table 1) and it will be reconfirmed that the patient continues to meet all of the Inclusion and none of the Exclusion criteria of the trial.

At the enrollment visit, the patient will have height and body weight recorded. This will be the baseline height and weight. To be eligible for the trial, a patient's baseline weight must be at least 15 kg. Height and weight will be monitored closely during the trial.

During the enrollment visit, the caregiver will administer the patient's first dose of setmelanotide via subcutaneous (SC) injection under the supervision of the trial staff. Patients' caregivers will be issued and instructed on the use of an electronic diary to capture daily compliance with injections.

All patients will begin treatment with setmelanotide at a dose of 0.5 mg per day. Patients will then increase their dose by 0.5 mg increments, every 2 weeks, as described in the SoA (Table 1). The maximum dose level of setmelanotide used in this trial will be based on the weight bands for the 2- to <6-year-old patients to support an exposure similar to that observed for adults dosed at 2 to 3 mg setmelanotide once daily (QD). The maximum dose level in this trial for patients who weigh <20 kg, [REDACTED] will be 0.5 mg, 1.0 mg, 1.5 mg and 2.0 mg QD, respectively.

If a patient's weight decreases to below 15 kg during the trial, the Investigator and Sponsor will discuss the patient's status and will jointly determine if a patient should continue the current dose, decrease the dose or discontinue treatment with setmelanotide temporarily or permanently. A dose reduction to 0.25 mg QD can be considered in such scenarios or in case of safety or tolerability concerns. These dose adjustments are considered adequate to help attain and maintain appropriate body weight in growing pediatric patients.

At the discretion of the Investigator, the dose escalation may be paused for a patient at any step prior to reaching their final maintenance dose, for safety or tolerability reasons, or due to achieving adequate weight loss. The dose may continue to be evaluated and adjusted, at the discretion of the Investigator, as long as the daily dose is kept between 0.25 mg and 2.0 mg QD, according to their respective weight. Patients will have trial visits approximately every 4 weeks through Week 20 and then approximately every 8 weeks through Week 52, and assessments will be performed as per the SoA (Table 1). Due to the young age of the patients, it may not be possible to perform all planned assessments at each visit. Thus, as described in the SoA (Table 1), the Investigator may adjust the planned assessments and blood draws as appropriate for the optimal medical care of the patients.

In specific, individual cases, dose escalation may be delayed compared to the originally planned schedule at enrollment, in order to mitigate potential tolerability issues (e.g., in case of gastrointestinal adverse events). If the escalation to the next dose level is delayed, the escalation period will be extended for that patient and the subsequent available site visits will then become "dose escalation" visits, where the appropriate and specific assessments related to the escalation visits will take place.

**End of Treatment**

The End of Treatment (EOT) will occur as an in-person clinic visit on Trial Week 52, which is the final day of treatment with setmelanotide. At the EOT, patients who are considered likely to benefit from continued setmelanotide treatment and who have completed this trial may be eligible to enter an open-label long-term extension (LTE) trial with setmelanotide. Patients and or caregivers/guardians must meet the eligibility criteria and should discuss eligibility with the Investigator. Eligible patients may participate in Bridging visits (every 12 weeks) (Table 1) if the LTE is not yet active.

All patients who discontinue treatment prematurely should attend an Early Termination of Treatment visit (ETT) as soon as possible after the last dose of trial treatment. Patients who discontinue treatment but remain enrolled in the trial should continue to complete all assessments (as Retained Dropouts). These patients will be required to complete the End of Study visit (EOS) as applicable following the

ETT (Section 5.1.5). Patients who discontinue treatment prematurely but remain enrolled and complete assessments through Week 52 are eligible to enroll in the optional LTE trial.

Patients who discontinue prematurely and withdraw from the trial will not be required to complete the EOS following the ETT. If the ETT visit occurs 4 weeks or later following the last dose of Setmelanotide, then the ETT visit will replace the EOS if no AEs are being monitored.

### End of Study

A final End of Study (EOS) visit will occur on Week 56 and may be conducted via telephone for patients who are not being monitored for an AE. The EOS visit is not required for patients who enroll in the LTE (or transition to Bridging visits prior to LTE).

At the Investigator's discretion and in consultation with the Sponsor, patients who have well tolerated setmelanotide, who are considered likely to benefit from continued treatment, and who have completed assessments through Week 52 may be offered continued setmelanotide treatment via:

- Enrollment in a separate LTE trial.
- Bridging visits until LTE availability (if the LTE trial is not active by the time of patient completion of this trial). See [Table 1](#).
- Commercial use of Setmelanotide QD, if applicable, according to the approved indication in their country, and in consultation with their prescribing physician

Completion of trial participation for an individual patient is defined as 1 of the following:

- For patients who complete trial treatment and enroll in the LTE: the in-person EOT visit at Week 52.
- For patients who complete treatment and do not enroll in the LTE: a Week 56 visit conducted via telephone.
- For patients who discontinue trial treatment prematurely and complete all assessments, but do not withdraw consent (and assent, as applicable): the latest of the Week 52 visit, the ETT visit, or EOS (if required).
- For patients who discontinue early and withdraw consent or assent: the ETT visit.

The end of the trial is defined as the date of the last visit of the last patient under the auspices of the current trial.

### Number of patients (planned):

The trial plans to enroll approximately 10-15 pediatric patients (approximately 5 or more with biallelic mutations of the *POMC*, *PCSK1*, or *LEPR* genes and approximately 5 or more with BBS) in a pivotal cohort. At the discretion of the Sponsor, if additional potential patients are identified, a supplemental cohort may be added to gain additional experience in this pediatric patient population.

### Diagnosis and criteria for inclusion and exclusion:

#### Inclusion Criteria

1. Patients must have obesity due to either:
  - a. *POMC*, *PCSK1*, or *LEPR* deficiency, confirmed by genetic testing demonstrating biallelic variants that are interpreted as pathogenic, likely pathogenic, or of undetermined significance (VUS) by the American College of Medical Genetics and Genomics (ACMG) criteria, **or**
  - b. BBS as defined by both (1) the Beales Criteria, 1999 ([Beales 1999](#); [Appendix 1](#)) AND (2) genetic confirmation of homozygous or compound heterozygous loss-of-function mutation in BBS genes.
2. Age between 2 to <6 years at the time of informed consent.

3. Obesity, defined as body mass index (BMI)  $\geq 97^{\text{th}}$  percentile for age and gender AND body weight of at least 15 kg at the time of enrollment.
4. Symptoms or behaviors of hyperphagia at any time during the patient's life, as determined by the Investigator at screening.
5. Parent or guardian of patient is able to communicate well with the Investigator, to understand and comply with the requirements of the trial (including once daily (QD) injection regimen and all other trial procedures) and is able to understand and sign the written consent.

**Exclusion Criteria:**

1. HbA1c  $>9.0\%$  at screening
2. History of significant liver disease other than non-alcoholic fatty liver disease (NAFLD) or nonalcoholic steatohepatitis (NASH).
3. Glomerular filtration rate (GFR)  $<60$  mL/min/1.73 m^2.
4. History or close family history (parents or siblings) of melanoma, or patient history of oculocutaneous albinism.
5. Significant dermatologic findings relating to melanoma or pre-melanoma skin lesions (excluding non-invasive basal or squamous cell lesion), determined as part of a comprehensive skin evaluation performed by the Investigator during screening. Any concerning lesions identified during screening will be biopsied and results known to be benign prior to enrollment.
6. Patient is, in the opinion of the Investigator, not suitable to participate in the trial.
7. Participation in any clinical trial with an investigational drug/device within 3 months prior to the first day of dosing.
8. Previously enrolled in a clinical trial involving setmelanotide or any previous exposure to setmelanotide.
9. Significant hypersensitivity to any excipient in the trial drug.
10. Abnormal hepatic function as evidenced by elevated Aspartate Aminotransferase (AST) and Alanine Aminotransferase (ALT) values  $>5x$  upper limit of normal (ULN).
11. Any other uncontrolled endocrine, metabolic or medical condition(s) known to impact body weight that could potentially interfere with interpretation of trial results.

**Investigational product, dosage and mode of administration:**

**Investigational product:** Setmelanotide, 10 mg/mL in a sterile solution for injection

**Dosage:** Between 0.5 and 2.0 mg/day (if a dose of 0.5 mg/day is not tolerated or if weight decreases to below [REDACTED])

**Mode of administration:** SC injection

**Duration of treatment:** Total treatment with setmelanotide will be 52 weeks. Total participation in the trial will last up to 64 weeks, including the Screening Period and the EOS visit.

**Criteria for Evaluation:****Primary Endpoints:**

- The proportion of patients demonstrating response to setmelanotide, defined as a decrease from baseline to 52 weeks in the patient's body mass index (BMI) z-score of  $\geq 0.2$ .
- Mean percent change in BMI from baseline to Week 52.

**Secondary Endpoints:**

- The following endpoints will be summarized and reported as change from baseline to 52 weeks:
  - Mean absolute change in BMI z-score per age and gender
  - Mean change in percent of the 95th percentile of BMI per age and gender
  - The mean change in vital signs and laboratory evaluations
  - The mean change in bone age
  - Mean change in Ages & Stages Questionnaires, Third Edition (ASQ®-3)
- Frequency and severity of AEs will also be summarized and reported during trial conduct.

**Statistical methods:**

Details of all statistical analyses will be described in a separate statistical analysis plan (SAP). The trial plans to enroll approximately 10-15 pediatric patients (approximately 5 or more patients with biallelic mutations of the POMC, PCSK1 or LEPR genes and approximately 5 or more patients with BBS). The sample size is not driven by statistical power considerations, but is primarily driven by clinical and practical considerations.

The primary objective is to evaluate the effect of setmelanotide on weight-related parameters, measured in terms of the response rate to setmelanotide. Due to the small sample size of the trial, no statistical hypothesis testing is planned, and efficacy will be reported using descriptive statistics. The safety population, including all patients who receive at least 1 dose of setmelanotide, will be used as the primary analysis population for all the analyses.

AEs will be coded by preferred term (PT) and system organ class (SOC) using the latest version of the Medical Dictionary for Regulatory Activities (MedDRA). All AE data will be presented in a data listing. Treatment-emergent AEs will be summarized by severity and relationship to trial drug. Serious AEs and AEs leading to early discontinuation will also be presented in data listings.

Actual values and changes from baseline for clinical laboratory test results, vital sign measurements etc., will be summarized using descriptive statistics (N, mean, standard deviation, median, minimum, and maximum). Shift tables will be generated for clinical laboratory test results. Clinical laboratory test results, vital sign measurements etc., will be presented in data listings.

The secondary objectives are to evaluate the efficacy of setmelanotide on weight-related parameters, as well as the safety and tolerability of setmelanotide.

No statistical hypothesis was made. The collected parameters will be summarized with appropriate descriptive statistics.

Due to the small sample size, summary statistics by genotype may be provided as appropriate.

## 2. SCHEDULE OF ASSESSMENTS

**Table 1: Schedule of Assessments**

Assessment	Screening	Enrollment Visit (Baseline)	Dose Escalation Visits 	Trial Visits 	EOT	EOS 	ETT	Bridging Visits
Trial Week	-8 to -1		2, 4, 6	8, 12, 16, 20, 28, 36, 44 	52	56		Q12 Weeks (If needed, In Person)
Trial Day	-56 to -1	1	15, 29, 43	57, 85, 113, 141, 197, 253, 309	365	393		
Window			±3	±5	±5	±3		
Informed Consent	X							
Inclusion/ Exclusion	X	X						
Medical History	X	X						
Physical Examination 	X	X*	X	X	X		X	X
Fitzpatrick classification scale		X			X		X	
Comprehensive Skin Examination 	X	X		X	X		X	X
Weight 	X	X	X	X	X		X	X
Height 	X	X	X	X	X		X	X
Vital Signs 	X	X	X	X	X		X	X
ECG 	X	X	X	X (W8 and 44)	X		X	X
Daily drug compliance 		X	X	X	X		X	
Genetic Sample 		X						
Safety Lab Tests 	X	X	X	X	X		X	X

**Table 1: Schedule of Assessments**

Assessment	Screening	Enrollment Visit (Baseline)	Dose Escalation Visits 	Trial Visits 	EOT	EOS 	ETT	Bridging Visits
Trial Week	-8 to -1		2, 4, 6	8, 12, 16, 20, 28, 36, 44 	52	56		Q12 Weeks (If needed, In Person)
Trial Day	-56 to -1	1	15, 29, 43	57, 85, 113, 141, 197, 253, 309	365	393		
Window			±3	±5	±5	±3		±5
Anti-Drug Antibodies 	X			X	X		X	X
Adverse events	X	X	X	X	X	X	X	X
Injection site inspection		X	X	X	X		X	X
Concomitant medication Review	X	X	X	X	X	X	X	X
Optional Nutritional Counseling 		X	X	X	X			X
Bone Age 		X			X			

**Table 1: Schedule of Assessments**

Assessment	Screening	Enrollment Visit (Baseline)	Dose Escalation Visits 	Trial Visits 	EOT	EOS 	ETT	Bridging Visits
Trial Week	-8 to -1		2, 4, 6	8, 12, 16, 20, 28, 36, 44 	52	56		Q12 Weeks (If needed, In Person)
Trial Day	-56 to -1	1	15, 29, 43	57, 85, 113, 141, 197, 253, 309	365	393		
Window			±3	±5	±5	±3		
Ages & Stages Questionnaires, Third Edition (ASQ-3) 		X		X	X			X
Dispense Trial Drug		X	X	X	X**			X
Return Trial Drug			X	X	X		X	X

Abbreviations: ECG=electrocardiogram; EOS=End of Study; EOT=end of treatment; ETT=Early Termination of Treatment; [REDACTED]; LTE=Long-term extension; [REDACTED]

\*Note: If there are <2 weeks between screening and enrollment, the enrollment visit physical examination may be waived.

\*\*Drug is dispensed at the EOT only for patients who continue to the Bridging visits.

 Patients should attend dose-escalation visits as appropriate per their respective escalation regimen, which is dictated by their weight, until achieving maximum dose level. See Section 7.3 for details.

 The dose may continue to be evaluated and adjusted, at the discretion of the Investigator, in 0.5 mg increments, so long as the daily dose is kept between 0.5 mg and the weight-based maximum for the patient (see Table 3).

 EOS visit should occur within 4 weeks of the last dose of study drug for patients who either discontinue prematurely or for patients who are being monitored for an adverse event (AE) after the EOT. This visit is not required for patients who complete the Week 52 visit and either enroll in the LTE or transition to Bridging visits.

 A complete physical examination will be conducted at screening and at the EOT visit. At other timepoints, an abbreviated examination will be performed. The abbreviated examination should focus on heart, lungs, skin, neurologic exam, and any areas of previous abnormal findings, noting any changes from baseline. Tanner staging should be performed at Screening and at the EOT (Week 52) visit. It may be done at additional visits, at the discretion of the Investigator

 A comprehensive skin evaluation will be performed by the Investigator or qualified designee. The skin exam should include a full body skin exam (head-to-toe skin examination). Any concerning lesions identified during the Screening Period will be biopsied and results known to be benign prior to the first dose of setmelanotide. If the pre-treatment biopsy results are of concern, the patient will be excluded from the trial. Additionally, any new lesion or change in an existing lesion identified during the course of the trial must be evaluated by a dermatologist and biopsied, if clinically indicated in the opinion of the dermatologist.

 Weight (kg) is to be measured at the clinic using the same scale throughout the trial or at home (during virtual visits or visiting nurse visits) using the same scale provided to the patient as part of the clinical trial. Weight should be measured after patients have attempted to empty their bladders and after fasting for

at least 8 hours. Patients are to wear light clothing or underwear and no shoes, with empty pockets, and will be weighed at approximately the same time of day. All measurements will be recorded to the nearest tenth kg if reported with a digital scale, or half kg with a mechanical scale.

7 Height (cm) will be measured, without shoes, socks or hats, using a wall-mounted stadiometer. The stadiometer should be calibrated by site personnel on a daily basis prior to height assessment. All measurements will be done in triplicate at each time point and recorded to the nearest half cm.

8 [REDACTED]

9 All blood pressure (BP) and heart rate (HR) measurements are to be obtained in a sitting position following at least 5 minutes of rest. All measurements will be taken in triplicate, approximately 2 minutes apart. When possible, BP should be taken in the non-dominant arm using the same methodology (automated or manual) throughout the trial.

10 A single 12-lead ECG will be performed. If an ECG is not practical in a young patient, it may be replaced by a rhythm strip and HR and PR interval should be documented.

11 A daily question querying whether the patient completed their daily injection will be asked via electronic diary. Paper versions can be used, if required.

12 Safety laboratory tests will include CBC with platelet count and standard indices, chemistry panel (includes sodium, potassium, chloride, CO2, albumin, total protein, glucose, BUN, creatinine, uric acid, aspartate aminotransferase (AST), alanine aminotransferase (ALT), gamma-glutamyl transferase (GGT), creatine phosphokinase (CPK), alkaline phosphatase, total bilirubin, direct bilirubin, lactate dehydrogenase (LDH), calcium, phosphorus), thyroid- stimulating hormone (TSH) and urinalysis with microscopic analysis if positive findings on dipsticks warrant further examination. Due to the age of the children, it may not be possible to collect samples (including urine samples) for all laboratory tests at every study visit. Screening may be performed over multiple days, to complete the required assessments. After enrollment, if all laboratory tests are not possible, then the tests should be collected in the following descending order of priority: safety, anti-drug antibodies, [REDACTED], [REDACTED] and then [REDACTED]. If it is not possible to collect the safety laboratory tests on two consecutive visits, the patient should be discussed with the Sponsor. If there is a marginal value close to the exclusion range, it is suggested to repeat the laboratory analyses at Investigator's discretion. To allow for pre- and post-dose sampling, patients will attend the site visit having fasted for an 8-hour time period without injecting the trial product. On the day of the site visit, dosing will be conducted on site. The Investigator's will adhere to the site-specific blood volume limits for safety laboratory and [REDACTED] to ensure minimal distress to the pediatric patients. If the genetic sample cannot be collected at the enrollment visit, it may be collected during a later trial visit. Anti-drug antibody samples (Section 8.5) are to be collected prior to dosing with setmelanotide. [REDACTED]

13 [REDACTED]

14 [REDACTED]

15 [REDACTED]

16 [REDACTED]

17 [REDACTED]

-  Bone age may be read locally initially, but the Sponsor may request central reading of images. A standard bone age measurement (of the hand/wrist area) will be obtained at the beginning and the end of the trial to monitor for growth related safety concerns.
-  The ASQ-3 is intended for use at six-month intervals for patients between 6 months and 3 years of age, and then at 1-year intervals through age 5. Thus, for patients who enter the trial at ages between 2 years and 3 years, the ASQ-3 should be administered at the Baseline visit, Week 28 visit and EOT visit. For patients who enter the trial between the ages of 3 and 6 years old, the ASQ-3 should only be administered at the Baseline visit and EOT visit.
-  A blood sample will be obtained at baseline to confirm a genetic diagnosis. However, patients may be entered into the trial with documentation of previously obtained genetic results.

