#### 5.1.3. Enrollment and trial procedures

At the enrollment visit, patients will undergo all procedures as outlined in the SoA ([Table 1](#)) and it will be reconfirmed that the patient continues to meet all of the Inclusion and none of the Exclusion criteria of the trial.

At the enrollment visit, the patient will have height and body weight recorded. This will be the baseline height and weight. To be eligible for the trial, a patient's baseline weight must be at least 15 kg. Height and weight will be monitored closely during the trial.

During the enrollment visit, the caregiver will administer the patient's first dose of setmelanotide via subcutaneous (SC) injection under the supervision of the trial staff. Patients' caregivers will be issued an electronic diary to capture daily compliance with injections.

All patients will begin treatment with setmelanotide at a dose of 0.5 mg per day. Patients will then increase their dose by 0.5 mg increments, every 2 weeks, as described in the SoA ([Table 1](#)). The maximum dose level of setmelanotide used in this trial will be based on the weight bands for the 2- to <6-year-old patients to support an exposure similar to that observed for adults dosed at 2 to 3 mg setmelanotide QD. The maximum dose level in this trial for patients who weigh [REDACTED] will be 0.5 mg, 1.0 mg, 1.5 mg and 2.0 mg QD, respectively.

If a patient's weight decreases to below 15 kg during the trial, the Investigator and Rhythm Pharmaceuticals, Inc. (henceforth Sponsor) will discuss the patient's status and will jointly

determine if a patient should continue the current dose, decrease the dose or discontinue treatment with setmelanotide temporarily or permanently. A dose reduction to 0.25 mg QD can be considered in such scenarios or in case of tolerability concerns, including for example, the occurrence of severe renal impairment. These dose adjustments are considered adequate for the pediatric patients to grow in height at a normal rate and support attaining and maintaining an appropriate body weight.

At the discretion of the Investigator, the dose escalation for a patient may be temporarily paused at any step prior to reaching their final maintenance dose, for safety or tolerability reasons, or due to achieving adequate weight loss. The dose may continue to be evaluated and adjusted, at the discretion of the Investigator, so long as the daily dose is kept between 0.25 mg and 2.0 mg QD, according to their respective weight.

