### 7.3. Treatment Administration

Setmelanotide will be administered as a SC injection. All patients will begin treatment at a dose of 0.5 mg of setmelanotide per day. Patients will then increase their dose by 0.5 mg increments, every 2 weeks, as described in the SoA (Table 1). The maximum dose level of setmelanotide used in this trial will be based on the weight bands for the 2- to <6-year-old patients to support an exposure similar to that observed for adults dosed at 2 to 3 mg setmelanotide QD. The maximum dose level in this trial for patients who weigh [REDACTED] will be 0.5 mg, 1.0 mg, 1.5 mg and 2.0 mg QD, respectively.

If a patient's weight decreases to below 15 kg during the trial, the Investigator and Sponsor will discuss the patient's status and will jointly determine if a patient should continue the current dose, decrease the dose or discontinue treatment with setmelanotide temporarily or permanently. A dose reduction to 0.25 mg can be considered in such scenarios or in case of safety or tolerability concerns. These dose adjustments are considered adequate to help attain and maintain appropriate body weight in growing pediatric patients.

At the discretion of the Investigator, a patient may temporarily pause the dose escalation at any step prior to reaching their final maintenance dose, for safety or tolerability reasons, or due to achieving adequate weight loss. The dose may continue to be evaluated and adjusted, at the

discretion of the Investigator, as [REDACTED] and 2.0 mg QD, according to their respective weight.

During the Dose Escalation visits (Weeks 2, 4 and 6 in SoA), the dose is to be increased as appropriate for the individual patient's weight at enrollment. At each visit, the decision to escalate the dose is to be based on patients' tolerability and health status. If a patient has already achieved their final maintenance dose prior to Week 4 or 6, the subsequent visits will not be considered "dose escalation" visits, but rather standard visits.

It is recommended to maintain a 2-week interval between the dose escalations, although the dose may be escalated at a longer interval (i.e., within 4 weeks), depending on patient weight and tolerability.

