### **8.2. Efficacy Assessments**

#### **8.2.1. Weight and Height**

Weight (kg) and height (cm) will be recorded at the time points designated in the SoA ([Table 1](#)). All measurements will be done in triplicate at each time point.

Weight should be measured after patients have attempted to empty their bladders and after fasting for at least 8 hours. Patients are to wear light clothing or underwear and no shoes, with empty pockets, and will be weighed at approximately the same time of day. All measurements will be recorded to the nearest 10th of a decimal place if reported with a digital scale, or half kg with a mechanical scale.

Whenever possible, the same scale should be used throughout the trial, including the Screening visit, and should be calibrated on a regular basis per manufacturer's specifications.

Patient's weight will be monitored closely during the trial. If a patient's weight decreases to below 15 kg, the Investigator and Sponsor will discuss the patient's status and will jointly determine if that patient should continue the current dose, decrease the dose or discontinue treatment with setmelanotide temporarily or permanently. A dose reduction to 0.25 mg QD can be considered in such scenarios or in case of tolerability concerns. These dose adjustments are considered adequate to help attain and maintain appropriate body weight in growing pediatric patients

Height (cm) will be measured without shoes, socks, or hats, using a wall-mounted stadiometer. The stadiometer should be calibrated by site personnel on a daily basis prior to height assessment. All measurements will be done in triplicate at each time point and recorded to the nearest half centimeter. Both weight and height measurements will be used to determine BMI and BMI-related assessments (i.e., Z-score and percentiles).

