  - 14. Based on the age and status of the patient, optional nutritional counseling may be requested by the Investigator, either during the enrollment visit or at any other time during the study. For pediatric patients, nutritional counseling will be performed by an appropriate dietician or nutritionist (or equivalent) to ensure that pediatric patients have adequate nutritional intake to maintain proper growth and development.
  - 15. Bone age may be read locally initially, but the Sponsor may request central reading of images. A standard bone age measurement (of the hand/wrist area) will be obtained at the beginning and the end of the study to monitor for growth related safety concerns.
  - 16. The ASQ-3 is intended for use at six-month intervals between 6 months and 3 years of age, and then at one-year intervals through age 5. Thus, for patients who enter the study at ages between 2 years and 3 years, the ASQ-3 should be administered at the Baseline Visit, Week 28 visit and End-of-Treatment Visit. For patients who enter the study between the ages of 3 and 6 years old, the ASQ-3 should only be administered at the Baseline Visit and End-of-Treatment Visit.
  - 17. The dose may continue to be evaluated and adjusted, at the discretion of the Investigator, in 0.5 mg increments, so long as the daily dose is kept between 0.5 mg and the weight-based maximum for the patient (see [Table 3](#)).
- 

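### The schedule footnote and the body text give different lower limits (0.5 mg and 0.25 mg) for Investigator-discretion dose adjustment, in the protocol and again in the SAP

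*Protocol*

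**What the plan says.** **Schedule footnotes.** Protocol Table 1 footnote 2 is attached to the Trial Visits column (Weeks 8 to 44). It permits continued adjustment in 0.5 mg increments, "so long as the daily dose is kept between 0.5 mg and the weight-based maximum for the patient". SAP Section 16.1 footnote 17 repeats it: "in 0.5 mg increments, so long as the daily dose is kept between 0.5 mg and the weight-based maximum for the patient". Neither footnote states an exception.

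**Body text, general range.** The protocol synopsis (enrollment and trial procedures) gives the Investigator the same discretion, "as long as the daily dose is kept between 0.25 mg and 2.0 mg QD, according to their respective weight". Section 5.1.3 agrees: "so long as the daily dose is kept between 0.25 mg and 2.0 mg QD, according to their respective weight". Neither names a step size in that sentence.

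**Body text, specific reduction.** The synopsis adds, after discussing weight below 15 kg: "A dose reduction to 0.25 mg QD can be considered in such scenarios or in case of safety or tolerability concerns". Section 7.3 has "A dose reduction to 0.25 mg can be considered in such scenarios or in case of safety or tolerability concerns" and Section 8.2.1 has "A dose reduction to 0.25 mg QD can be considered in such scenarios or in case of tolerability concerns". Section 5.1.3 and SAP Section 3.3 carry equivalent sentences.

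**Weight band.** The synopsis sentence that begins "The maximum dose level in this trial for patients who weigh <20 kg" goes on to list 0.5, 1.0, 1.5 and 2.0 mg in band order. The lowest band therefore has a maximum of 0.5 mg. The other bands are redacted.

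**The concern.** The footnotes and the range sentences in the synopsis and Section 5.1.3 describe one activity: ongoing dose adjustment by the Investigator. They set different floors, and the footnotes add a step size that cannot produce 0.25 mg. Protocol Section 8 says that adherence to the requirements in the schedule is essential, so the footnote cannot be dismissed as a mere summary.

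Two things are at stake. An Investigator who is considering a reduction has two incompatible instructions about whether 0.25 mg is allowed. And SAP Section 7 lists every departure from protocol procedures as a deviation, but whether a 0.25 mg dose is a departure depends on which passage is applied.

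**Working it through.** No sample-size or power figure is involved. The check sets the passages side by side and asks whether 0.25 mg fits each one.

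| Place | Floor for discretionary adjustment | Step | Separate 0.25 mg reduction |
|---|---|---|---|
| Protocol synopsis, enrollment and trial procedures | 0.25 mg | not stated in that sentence | yes |
| Protocol 5.1.3 | 0.25 mg | not stated in that sentence | yes |
| Protocol 7.3 | redacted | not stated in that sentence | yes |
| Protocol 8.2.1 | no range given | – | yes |
| Protocol Table 1 footnote 2 | 0.5 mg | 0.5 mg | none mentioned |
| SAP 3.3 | redacted | not stated in that sentence | yes |
| SAP 16.1 footnote 17 | 0.5 mg | 0.5 mg | none mentioned |

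**Step 1: can 0.25 mg occur under the footnote?** All patients start at 0.5 mg. With 0.5 mg steps and a 0.5 mg floor, the possible doses are 0.5, 1.0, 1.5 and 2.0 mg, up to the patient's maximum. One step down from 0.5 mg is 0.5 − 0.5 = 0, so 0.25 mg is never reached. One step up from 0.25 mg is 0.25 + 0.5 = 0.75 mg, which is not one of those dose levels. The step-size conflict follows from the same footnote and is not a separate defect.

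**Step 2: what does each text leave, by weight-based maximum?** The body text's upper end is read here as capped at the patient's own maximum, because it refers to the patient's weight.

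| Maximum dose | Footnote 2 permits | Synopsis and 5.1.3 permit |
|---|---|---|
| 0.5 mg (under 20 kg) | 0.5 mg only | 0.25 to 0.5 mg |
| 1.0 mg | 0.5, 1.0 mg | 0.25 to 1.0 mg |
| 1.5 mg | 0.5, 1.0, 1.5 mg | 0.25 to 1.5 mg |
| 2.0 mg | 0.5, 1.0, 1.5, 2.0 mg | 0.25 to 2.0 mg |

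In the lowest band the footnote's range runs from 0.5 to 0.5 mg, so discretionary adjustment has no content. Eligibility starts at 15 kg, so the group concerned at entry is 15 to under 20 kg.

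**Step 3: is this a general rule with an exception?** The reduction sentences alone could be read as an exception to a 0.5 mg floor. The range sentences in the synopsis and Section 5.1.3 do not fit that reading, because they put 0.25 mg inside the general discretionary range.

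**The case against.** The strongest reply is that 0.5 mg is the routine floor and 0.25 mg a conditional reduction. There is support for this. The synopsis dosage line gives 0.5 to 2.0 mg/day, followed by a condition about intolerance of 0.5 mg or falling weight. The reduction sentences are conditional too. Redactions could also hide a qualifier: the rest of that dosage line, the lower bounds in Section 7.3 and SAP Section 3.3, and parts of Table 3, to which footnote 2 refers. So the exception reading cannot be excluded as an account of what was intended. It still does not reconcile the visible text, for the reason in step 3 of the working and because neither footnote signals an exception.

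Three stronger readings are tempting, and the documents do not support them:

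- **That the SAP as a whole takes the 0.5 mg side.** Only footnote 17 does. SAP Section 3.3 allows a reduction to 0.25 mg, so the SAP has the same internal split as the protocol.
- **That sites will follow the footnote and so cannot reduce the dose.** Nothing says that sites work from the schedule alone. The 0.25 mg option appears in several body sections. Below 15 kg the Investigator and Sponsor decide jointly, and immediate safety concerns go to the Sponsor. The ambiguity is sharpest for ordinary tolerability reductions.
- **That exposure results or discontinuation counts will be distorted.** SAP Section 10.2.1 sums the dose actually received and Section 10.2.4 lists each dose change with its reason, so either practice would be recorded. Any effect on discontinuation is conjecture.

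**Conclusion.** The point holds as an internal inconsistency: within each document, the schedule footnote and the body text disagree on whether 0.25 mg is permitted. The protocol conflict is the one that bears on sites, since the SAP is an analysis document. The floors are 0.25 mg and 0.5 mg. For children under 20 kg this is the difference between a range and a single permitted dose.

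The documents do not say how many children will fall in that band. With 10 to 15 patients planned, each child is 1/15 = 6.7% to 1/10 = 10% of the sample. The efficacy analyses are descriptive, and no bias in them is claimed.

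The conclusion rests on the unredacted text only, and on reading the synopsis list as pairing the under-20 kg band with its first dose. It should be corrected because it is an operative dosing instruction with safety relevance. No view is taken on which limit is right.

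**What to change.** Reconcile these places so that one dose range and one step size appear throughout, or so that any exception to the general range is stated in the footnotes themselves:

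- Protocol synopsis: the enrollment and trial procedures text (both the range and the reduction sentence) and the dosage line
- Protocol Table 1 footnote 2
- Protocol Sections 5.1.3, 7.3 and 8.2.1
- SAP Section 3.3 and Section 16.1 footnote 17

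The sponsor's clinical team must decide which limit and step size are intended. The reconciled text would also settle whether a 0.25 mg dose is a protocol deviation. The cost is a protocol clarification and a matching SAP edit, with no new procedures.
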